#### CLW Visit 4 – Lens Order 2 Follow-up & Order 3 Dispensing (Visit 2 + 10±3 days)

The routine below will be followed:

- Concomitant treatments questionnaire (Questionnaire B)
- Visual satisfaction and contact lens wearing characteristics questionnaire (Questionnaire D)
- Over refraction (best sphere monocular & binocular) distance and near
- Standard Snellen visual acuity at distance (monocular & binocular) distance and near
- [REDACTED]
- [REDACTED]
- Visual satisfaction questionnaire following iPad use vision activities (Questionnaire D)
- Contact lens fit clinical evaluation
- STUDY CONTACT LENS REMOVAL (ORDER 2)
- Safety ocular integrity examination
- STUDY CONTACT LENS INSERTION & WEAR 15 MINUTES (ORDER 3)
- Over refraction (best sphere monocular & binocular) distance and near
- Standard Snellen visual acuity at distance (monocular & binocular) distance and near
- Decision to dispense contact lenses or try an alternative prescription
- Contact lens fit clinical evaluation
- Decision to dispense contact lenses
- Dispensing of Study product
- Contact lens usage instruction

 Randomly as per the randomization scheme in place; one of the two test contact lenses or the control contact lens.

 If an alternative prescription is tried the routine above will be repeated. Up to three attempts will be allowed.

 If the contact lens fit is not suitable for dispensing the participant will be discharged from the study.

 Randomly as per the randomization scheme in place; one of the two test contact lenses or the control contact lens.

 If an alternative prescription is tried the routine above will be repeated. Up to three attempts will be allowed.

 If the contact lens fit is not suitable for dispensing the participant will be discharged from the study.

- Scheduling

#### CLW Visit 5 – Lens Order 3 Follow-up and Exit (Visit 3 + 10±3 days)

The routine below will be followed:

- Concomitant treatments questionnaire (Questionnaire B)
- Visual satisfaction and contact lens wearing characteristics questionnaire (Questionnaire D)
- Over refraction (best sphere monocular & binocular) distance and near
- Standard Snellen visual acuity at distance (monocular & binocular) distance and near
- [REDACTED]
- [REDACTED]
- Visual satisfaction questionnaire following iPad use vision activities (Questionnaire D)
- Contact lens fit clinical evaluation
- STUDY CONTACT LENS REMOVAL (ORDER 3)
- Preference questionnaire (Questionnaire E)
- Safety ocular integrity examination
- Discharge

#### 6.6 Non-Contact Lens Wearers (NW) Study Visit Routine

##### NW Visit 1 – Screening/ Enrolment /Baseline Visit/ Adaptation Contact Lens Dispensing

The routine below will be followed:

- Explanation of the study
- Signing of the consent form
- Participant demographics and ocular history questionnaire (Questionnaire A)
- Concomitant treatments questionnaire (Questionnaire B)
- Manifest Refraction (sphero-cylindrical & best sphere monocular and binocular) distance and near
- Standard Snellen/LogMAR visual acuity at distance (monocular & binocular) and near (with +2.00D add) with sphero-cylindrical and best sphere refractions
- Review of inclusion and exclusion criteria
- Ocular dominance measurement
- Pupil size measurements
- [REDACTED]
- [REDACTED]
- iPad tasks familiarization
- Safety ocular integrity examination
- PROCLEAR SPHERICAL CONTACT LENS INSERTION & WEAR 15 MINUTES
- Over refraction (best sphere monocular & binocular) distance and near
- Standard Snellen/LogMAR visual acuity at distance (monocular & binocular) distance and near
- Decision to accept contact lenses or try an alternative prescription
- Contact lens fit clinical evaluation
- Decision to continue with determination of eligibility

 All participants will attend the visit wearing spectacles.

 The participants and their parents / guardians will be given full details of the investigation at the time of making the appointment for the enrolment visit. The explanation at the time of the visit will be to reinforce the information given during the initial telephone contact and answer any questions the participants and their parents / guardians may have.

 Randomly as per the randomization scheme in place one of the two test contact lenses or the control contact lens

 If an alternative prescription is tried the routine above will be repeated. Up to three attempts will be allowed

- Contact lens usage instruction with participants and parents/guardians
- Scheduling

#### NW Visit 2 – Adaptation Contact Lens Follow-up & Order 1 Dispensing (Visit 1+ 14±7 days)

The routine below will be followed:

- Concomitant treatments questionnaire
- Visual satisfaction and contact lens wearing history questionnaire (Questionnaire C)
- Over refraction (best sphere monocular & binocular) distance and near
- Standard Snellen visual acuity at distance (monocular & binocular) distance and near
- Contact lens fit clinical evaluation
- PROCLEAR SPHERICAL CONTACT LENS REMOVAL
- Safety ocular integrity examination
- BREAK 15 MINUTES
- STUDY CONTACT LENS INSERTION (ORDER 1) & WEAR 15 MINUTES
- Over refraction (best sphere monocular & binocular) distance and near
- Standard Snellen/LogMAR visual acuity at distance (monocular & binocular) distance and near
- Decision to dispense contact lenses or try an alternative prescription
- Contact lens fit clinical evaluation
- Decision to dispense contact lens
- Dispensing of Study product
- Contact lens usage instruction with participants and parents/guardians
- Scheduling

#### NW Visit 3 – Order 1 Follow-up & Order 2 Dispensing (Visit 2+ 10±3 days)

The routine below will be followed:

- Concomitant treatments questionnaire (Questionnaire B)
- Visual satisfaction and contact lens wearing characteristics questionnaire (Questionnaire D)
- Over refraction (best sphere monocular & binocular) distance and near
- Standard Snellen visual acuity at distance (monocular & binocular) distance and near
- [REDACTED]
- [REDACTED]
- Visual satisfaction questionnaire following iPad use vision activities (questionnaire D)
- Contact lens fit clinical evaluation
- STUDY CONTACT LENS REMOVAL (ORDER 1)
- Safety ocular integrity examination
- STUDY CONTACT LENS INSERTION & WEAR 15 MINUTES (ORDER 2)
- Over refraction (best sphere monocular & binocular) distance and near
- Standard Snellen visual acuity at distance (monocular & binocular) distance and near
- Decision to dispense contact lenses or try an alternative prescription
- Contact lens fit clinical evaluation
- Decision to dispense contact lens

 Randomly as per the randomization scheme in place; one of the two test contact lenses or the control contact lens

 If an alternative prescription is tried the routine above will be repeated. Up to three attempts will be allowed

 If the contact lens fit is not suitable for dispensing the participant will be discharged from the study

 Randomly as per the randomization scheme in place one of the two test contact lenses or the control contact lens

 If an alternative prescription is tried the routine above will be repeated. Up to three attempts will be allowed

 If the contact lens fit is not suitable for dispensing the participant will be discharged from the study

- Dispensing of Study product
- Contact lens usage instruction
- Scheduling

#### NW Visit 4 – Order 2 Follow-up & Order 3 Dispensing (Visit 2+ 10±3 days)

The routine below will be followed:

- Concomitant treatments questionnaire (Questionnaire B)
- Visual satisfaction and contact lens wearing characteristics questionnaire (Questionnaire D)
- Over refraction (best sphere monocular & binocular) distance and near
- Standard Snellen visual acuity at distance (monocular & binocular) distance and near
- [REDACTED]
- [REDACTED]
- Visual satisfaction questionnaire following iPad use vision activities (questionnaire D)
- Contact lens fit clinical evaluation
- STUDY CONTACT LENS REMOVAL (ORDER 2)
- Safety ocular integrity examination
- STUDY CONTACT LENS INSERTION & WEAR 15 MINUTES (ORDER 3)
- Over refraction (best sphere monocular & binocular) distance and near
- Standard Snellen visual acuity at distance (monocular & binocular) distance and near
- Decision to dispense contact lenses or try an alternative prescription
- Contact lens fit clinical evaluation
- Decision to dispense contact lens
- Dispensing of Study product
- Contact lens usage instruction
- Scheduling

#### NW Visit 5 – Order 3 Follow-up Visit and Exit (Visit 3+ 10±3 days)

The routine below will be followed:

- Concomitant treatments questionnaire (Questionnaire B)
- Visual satisfaction and contact lens wearing characteristics questionnaire (Questionnaire D)
- Over refraction (best sphere monocular & binocular) distance and near
- Standard Snellen visual acuity at distance (monocular & binocular) distance and near
- [REDACTED]
- [REDACTED]
- Visual satisfaction questionnaire following iPad use vision activities (Questionnaire D)
- Contact lens fit clinical evaluation
- STUDY CONTACT LENS REMOVAL (ORDER 3)
- Safety ocular integrity examination
- Discharge

## 7 Statistical Analysis and Sample Size Determination

### 7.1 Margins of equivalence

 Randomly as per the randomization scheme in place one of the two test contact lenses or the control contact lens

 If an alternative prescription is tried the routine above will be repeated. Up to three attempts will be allowed

 If the contact lens fit is not suitable for dispensing the participant will be discharged from the study

For the primary endpoints the margin of equivalence for overall visual satisfaction will be 10 points on the 100-point visual analog scale and for daily wearing time 2.0 hours.

For the secondary endpoints the margin of equivalence for overall visual performance will be 0.05 logMAR and for specific activities visual satisfaction 10 points on the 100-point visual analog scales.

## 7.2 Determination of Sample Size

A sample size estimation has been carried out based upon an interim read in a previous study following a similar protocol

The sample size estimation has been carried out based upon an interim read in a previous study following a similar protocol. The analysis of the initial seven participants in that study produced for overall visual satisfaction after one week of wear a mean standard deviation of the difference between test and control in this study of 16.1 points on a the 100-point visual analog scale. Based upon the results of this previous study a sample size of 23 achieves 80% power and a significance level of 0.025 to detect non-inferiority using a one-sided t-test when the margin of equivalence is -10.0 and the true difference between the mean and the reference is 0.0.

The sample size estimation was carried out on the same data for daily wearing time; the mean standard deviation of the difference in daily wearing time between test and control in this study was 0.8 hours. Based upon these results a sample size of 8 achieves 87% power and a significance level Of 0.025 to detect non-inferiority using a one-sided t-test when the margin of equivalence is -1.0 hour and the true difference between the mean and the reference is 0.0.

Based upon the above estimates involving only seven participants likely to over-estimate variability, hence the aim in this study will be to achieve a per protocol population of at least 20 participants.

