Planned Start Date	1 Septmeber 2020
Overall Study Duration	Six months. This includes the study enrolment period, lens wear period of approximately three months and study close out.
Objective(s)	The primary objective of the study will be to: i. determine the level of overall visual satisfaction achieved with each contact lens type tested; ii. determine the habitual daily wearing time; The secondary objective will be to: i. measure the visual performance achieved with each contact lens types tested;

	
ii. determine the level of visual satisfaction during specific visual tasks.
																		
Hypotheses	
The primary hypotheses that will be tested will be that:
 
 
i. overall visual satisfaction with the test contact lens designs is not inferior to the control contact lens design;
 
ii. habitual daily wearing time with the test contact lens designs is not inferior to the control contact lens design.
 
 
The secondary hypotheses that will be tested will be that:
 
 
i. the visual performance with the test contact lens designs is not inferior to the control contact lens design;
 
ii. the level of visual satisfaction during specific visual tasks with the test contact lens designs is not inferior to the control contact lens design.
 
																		
Efficacy Endpoint (S)	
The primary endpoints will be:
 
 
i. Overall vision satisfaction recorded on a visual analog scale;
 
ii. Daily wearing time in hours.
 
 
The secondary endpoints will be:
 
 
i. logMAR visual acuity.
 
ii. Level of visual satisfaction during specific visual tasks recorded on visual analog scales ;
 
																		
Efficacy Procedures	
The primary efficacy procedures will be:
 
 
i. Measurement of overall visual satisfaction;
 
ii. Recording of habitual wearing time.
 
 
The secondary efficacy procedures will be:
 
 
i. Specialist visual performance measurement. using [REDACTED];
 
ii. Measurement of visual satisfaction during specific visual tasks.
 
																		

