## 7.3 Statistical Analysis Plan

A detailed statistical analysis plan will be developed before database closure.

For all the key parameters recorded, summary tables including descriptive and/or distribution statistics will be given for both the per-protocol analysis and the safety data sets.

All participants who meet the eligibility criteria, adhere to the protocol, and successfully complete the full study assessment will be available for the per-protocol analysis. Participants with missing data will be included in the analysis unless there is some non-response-related reason to exclude them, such as a protocol violation/invalid data.

For continuous variables, the following descriptive statistics will be reported: mean, median, standard deviation, quartiles, minimum, maximum and sample size. For nominal and ordinal variables distribution tables will be produced.

Normality testing will be performed for endpoints variables. All the continuous/ordinal endpoints analysed by way of comparative statistics will be checked for normality. The kurtosis and skewness values will be produced. The Q-Q Probability plot will be used to examine the values against the normal distribution. Statistical testing by Kolmogorov Smirnov and Shapiro Wilk tests will also be considered. If the normality assumption holds, a Linear Mixed Model will be used while, if the normality assumption does not hold, a Generalized Linear Mixed Model will be used.

For the primary analyses, the 2-sided 95% confidence interval for the difference between the test and control lenses will be produced, with non-inferiority being shown if the interval is entirely above -10.0 points for overall visual satisfaction and -2.0 hours for daily wearing time.

For the secondary analyses, the 2-sided 95% confidence interval for the difference between the test and control lenses will be produced, with non-inferiority being shown if the interval is entirely below +0.05 logMAR points for overall visual performance and if the interval is entirely above -10.0 points for specific activities visual satisfaction.

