## 13.3 Modifications to the Clinical Investigational Plan

Any modifications to the clinical investigational plan that are considered necessary can only be effected after approval from the principal investigator and the Independent Ethics Committee. In an emergency situation, as indicated in ISO14155, the clinical investigator will exercise his judgement to safeguard the participant's interest and may deviate from the clinical investigation plan without the prior approval of the Independent Ethics Committee. In that case, the deviation will not be considered as a breach of agreement but will be reported to the ethics committee.

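### The wearing-time power statement in section 7.2 uses a 1.0 hour margin, half the 2.0 hours set in 7.1 and applied in 7.3, so its 8 participants and 87% power do not describe the planned test

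*Combined protocol and SAP*

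**What the plan says.** The synopsis makes wearing time a primary hypothesis: "habitual daily wearing time with the test contact lens designs is not inferior to the control contact lens design". Three consecutive sections then give its margin.

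- **7.1 Margins of equivalence** sets the primary margins at "10 points on the 100-point visual analog scale and for daily wearing time 2.0 hours".
- **7.2 Determination of Sample Size** takes an SD of the test-control difference of 0.8 hours from seven participants in a previous study. It states that "a sample size of 8 achieves 87% power" in a one-sided t-test at 0.025, "when the margin of equivalence is -1.0 hour and the true difference between the mean and the reference is 0.0".
- **7.3 Statistical Analysis Plan** declares non-inferiority if the two-sided 95% confidence interval is "entirely above -10.0 points for overall visual satisfaction and -2.0 hours for daily wearing time".

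The satisfaction margin is 10 points in all three sections. Only the wearing-time margin changes. No section presents 1.0 hour as a sensitivity case or gives a reason for the difference.

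**The concern.** In a non-inferiority comparison the margin is the success criterion, so the margin used for planning should be the one used for the decision. Here the decision margin is twice the planning margin. Two things follow.

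First, the only power statement for this primary endpoint describes a test that will not be run.

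Secondly, a reader cannot tell whether 2.0 hours was a deliberate choice or whether 7.2 carries an older value. A lower confidence limit between -2.0 and -1.0 hours would pass under 7.3 and fail under the margin in 7.2. If the question were settled only after results by lens were known, the choice could look driven by the data.

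**Working it through.** **Inputs.** From 7.2: SD of the paired difference 0.8 h, one-sided alpha 0.025, true difference 0, n = 8, stated power 87%, margin 1.0 h, target per-protocol population of at least 20. From 7.1 and 7.3: margin 2.0 h. The two-sided 95% interval in 7.3 corresponds to one-sided 0.025, so alpha agrees between the sections.

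**Formula.** For a t-test on paired differences with margin M and true loss d:

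power = P(T > t(0.975, n-1)), where T is noncentral t with n-1 degrees of freedom and noncentrality (M - d)·√n / SD.

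**Step 1: reproduce the plan's figure.** With n = 8, M = 1.0, d = 0 and SD = 0.8, the noncentrality is 1.0 × √8 / 0.8 = 3.54 and the critical value is 2.365. Power is 85.6%. Over SDs that round to 0.8 (0.75 to 0.85), power runs from 89.6% down to 81.3%. An SD of 0.784 gives 87%, and any SD from 0.778 to 0.789 rounds to 87%. The stated figure is therefore consistent with a 1.0 h margin and a rounded SD. Other calculations at 1.0 h and n = 8 do not fit: a normal approximation gives 94.2%, one-sided alpha 0.05 gives 93.6%, and a two-sample t-test with 8 per arm gives 64.3%.

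**Step 2: put in the margin of 7.1 and 7.3.** With M = 2.0 the noncentrality doubles to 7.07 and power at n = 8 is 99.996%. It stays above 99.98% for every SD from 0.75 to 0.85. Three participants give 61.9% and four already give 89.9%. To obtain 87% at n = 8 the SD would have to be about 1.57 h, which does not round to 0.8. So the -1.0 is not merely a misprint: the 8 and the 87% were calculated with it, and changing only the margin in that sentence would leave both wrong.

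**Step 3: what each margin means at the target n = 20 (SD 0.8).** Probability of declaring non-inferiority:

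| True loss | Margin 1.0 h | Margin 2.0 h |
|---|---|---|
| 0 h | 99.96% | over 99.99% |
| 0.5 h | 75.5% | over 99.9% |
| 1.0 h | 2.5% | 99.96% |
| 1.5 h | about 0% | 75.5% |

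For SD 0.75 to 0.85, the 75.5% at a 0.5 h loss (margin 1.0 h) ranges from 80.7% to 70.4%. The 99.96% at a 1.0 h loss (margin 2.0 h) ranges from 99.99% to 99.87%. The chance of passing stays at 80% or more up to a true loss of 0.47 h with the 1.0 h margin and 1.47 h with the 2.0 h margin.

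In terms of the observed mean, the 95% interval half-width is 2.093 × 0.8 / √20 = 0.37 h. A test lens passes with an observed mean loss of up to about 2.0 - 0.37 = 1.63 h under 7.3, against 1.0 - 0.37 = 0.63 h under the margin in 7.2.

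**Step 4: effect on sample size.** Satisfaction (SD 16.1, margin 10) needs the larger sample: 23 participants give 81.2% by the same formula, in line with the stated 80%. Wearing-time power at n = 20, SD 0.8 and no true difference exceeds 99.9% with either margin, so the mismatch does not change n.

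**The case against.** The strongest reply is that the decision rule is not in doubt. The section that sets the margins and the section that states the success rule agree on 2.0 hours; 7.2 is a planning calculation and sets no criterion. An analyst following the text would apply -2.0 hours. That stands: it is the operative rule as written. The planning error is also conservative, since 7.2 understates the power of the planned test, and the sample size does not move. That stands too.

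The table of contents offers a hint about origin. It lists sample size as 7.1 and the analysis plan as 7.2, with no section on margins, which suggests that the margins section was added later and the power sentence was not updated. This makes a leftover sentence the likelier reading, but it does not show that 2.0 hours was considered and chosen.

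Part of the contrast at a true 1.0 hour loss holds by construction: at the margin itself the chance of passing equals alpha, here 2.5%. The comparison shows what doubling a margin does, and does not show that either value is wrong.

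The power figures also depend on an SD from seven participants, whose sampling error is far wider than rounding. If the SD were 1.6 (an assumption for illustration, twice the stated value), power at n = 20 and no true difference would be 75.5% with the 1.0 hour margin, and a true 1.0 hour loss would pass the 2.0 hour margin with probability 75.5% instead of 99.96%. The figures should be read as conditional on 0.8.

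None of this reconciles the sections. The margin of a primary endpoint still appears with two values, and the stated power belongs to the value that will not be used.

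**Conclusion.** Wrong as written. Sections 7.1 and 7.3 use 2.0 hours and 7.2 uses 1.0 hour for the same primary comparison, with no explanation. The 8 participants and 87% in 7.2 were calculated with 1.0 hour (85.6% at SD 0.8, 87% at 0.784); under the planned 2.0 hours the power at n = 8 is 99.996%. The target of 20 is not affected through this endpoint. What is affected is the meaning of success: at n = 20 the observed mean loss that still passes differs by 1.0 hour between the two margins.

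These results assume the SD of 0.8 hours and the paired t-test of 7.2. Section 7.3 plans a mixed model, so they approximate the final analysis. The contradiction itself rests on no assumption. The document does not show which margin was intended.

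**What to change.** Before data by lens are reviewed, the sponsor should confirm which margin is intended, give it identically in 7.1, 7.2 and 7.3 with a reason, and carry it into the later document ("A detailed statistical analysis plan will be developed before database closure"). The choice of value is the sponsor's.

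- **If 2.0 hours stands:** replace the wearing-time sentence in 7.2 with the power at -2.0 hours, which is over 99.9% at n = 8 and at n = 20 (SD 0.8, no true difference). The success criterion does not change.
- **If 1.0 hour was intended:** change the margin in 7.1 and the decision limit in 7.3 to 1.0 hour, and restate power at n = 20 as 99.96% at no true difference and 75.5% at a true loss of 0.5 hours (SD 0.8). This makes a primary criterion stricter; with the 2.0 hour margin the power at that loss is over 99.9%.

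In either case, say that the power is conditional on an SD estimated from seven participants.

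The cost is text only, with no extra participants, visits or analyses. Section 13.3 applies: modifications to the plan "can only be effected after approval from the principal investigator and the Independent Ethics Committee".

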## 1 Overall Synopsis

Study Sponsor	CooperVision Inc. [REDACTED]
Title of Study	Evaluation of The Clinical Acceptance and Performance of Soft Contact Lenses for Myopia Management
Protocol Number	ID20-28 / CVI: 20-51
Type of study	Single arm, prospective, 10 days wear of each study contact lenses (three contact lens types), randomized order of lens types usage, crossover study with investigator and participant masking.
Study Population	Required: 20 completed participants as per protocol (cohort). Planned: Up to 40 screened, with the aim of enrolling up to 30 participants.
Duration of study treatment	10 (±3) days of daily lens wear per study contact lens type.
Inclusion Criteria	In order to be enrolled, each participant shall meet the following criteria: i. Age 10 to 16 years; ii. Spectacle refraction: -0.75 to -6.00D spherical equivalent, maximum anisometropia 1.25D, cylinder up to -1.00DC iii. Best corrected visual acuity of at least 20/25 in each eye. iv. Parents/guardians and participant have read and understood the Participant Information Sheet; v. Parents/guardians and participant have read, signed and dated the Informed Consent; vi. Have normal eyes with the exception of the need for visual correction; vii. Be willing and able to adhere to the instructions set in the clinical protocol and maintain the appointment schedule.
Exclusion Criteria	The following are specific criteria that exclude a candidate from enrolment in this study: i. Ocular anterior segment infection, inflammation, abnormality, or active disease that would contraindicate contact lens wear; ii. Newly prescribed use of some systemic or ocular medications for which contact lens wear could be contraindicated as determined by the investigator; iii. Monocular participants (only one eye with functional vision) or participants fit with only one lens; iv. Subjects with slit lamp findings greater than grade 1 (e.g. edema, infiltrates, corneal neovascularization, corneal staining, tarsal abnormalities, conjunctival, anterior segment inflammation) as per ISO 11980, any previous history or signs of a contact lens related corneal inflammatory event (past corneal ulcers), or any other ocular abnormality that may contraindicate contact lens wear at the enrolment visit; v. History of herpetic keratitis, ocular surgery or irregular cornea; vi. Enrolment of the family members of the investigator, family members of the investigator's staff, or individuals living in the households of these individuals.

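### Section 7.2 calculates 23 participants for 80% power but requires only 20, where the plan's own inputs give 75%, and the reason given for the reduction does not hold

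*Combined protocol and SAP*

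**What the plan says.** Section 7.2 (Determination of Sample Size) takes its variability from an interim read of a previous study. The first seven participants there gave a "mean standard deviation of the difference between test and control in this study of 16.1 points". With a margin of -10.0 points, a true difference of zero and a one-sided t-test, the section reports that "a sample size of 23 achieves 80% power and a significance level of 0.025".

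The section ends with a smaller number, a minimum of 20. It describes the estimates as "involving only seven participants likely to over-estimate variability, hence the aim in this study will be to achieve a per protocol population", and it sets that minimum on this ground.

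The Synopsis (section 1, Study Population) carries the smaller figure: "Required: 20 completed participants as per protocol (cohort). Planned: Up to 40 screened, with the aim of enrolling up to 30 participants".

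Neither section states the power at 20, an alternative SD or an expected dropout rate.

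**The concern.** The calculation and the requirement do not match. The only power quoted for this primary endpoint belongs to 23 participants, and the study meets its plan with 20. The gap between 23 and 20 is visible, but its cost in power is not, and a reader may well attach the 80% to the study as a whole.

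The step down rests on one statement, that a seven-participant estimate probably overstates the variability. Small size alone does not push an SD upwards. If the argument fails, nothing else in the text supports going below the calculated number.

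What is at stake is an inconclusive result. With too few completers, the confidence interval for lenses that truly perform alike may cross -10 points, and that could be misread as a deficiency of the test lens. A false claim of non-inferiority does not become more likely.

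**Working it through.** **Inputs, all from section 7.2.** SD of the within-participant difference s = 16.1; margin 10; true difference 0; one-sided alpha 0.025; t-test. The design is a crossover, so the test is a one-sample t-test on paired differences. The rule in section 7.3 (two-sided 95% interval entirely above -10.0) is equivalent to one-sided 0.025.

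**Formula.** Power = P(T > t[0.975, n-1]), where T is noncentral t with n-1 degrees of freedom and noncentrality (10/16.1) × √n = 0.6211 × √n.

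**Reproducing the plan's 23, then power at other sizes.**

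| Completers | Noncentrality | Critical t | Power |
|---|---|---|---|
| 20 | 2.778 | 2.093 | 75.0% |
| 21 | 2.846 | 2.086 | 77.3% |
| 22 | 2.913 | 2.080 | 79.3% |
| 23 | 2.979 | 2.074 | 81.2% |
| 25 | 3.106 | 2.064 | 84.6% |
| 30 | 3.402 | 2.045 | 90.8% |

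The smallest n reaching 80% is 23, so the plan's figure reproduces exactly. A normal approximation would give 79.3% at 20 and a sample size of 21, but the plan names a t-test and its 23 is the t-test answer.

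**SD needed for 80% at 20.** Solving the same formula for s gives 15.14. Since 15.14/16.1 = 0.940, the true SD would have to be about 6% below the pilot value.

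**Does an SD from seven participants tend to be too high?** Assume normal differences and 6 degrees of freedom.

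- Expected SD relative to the true SD: c4 = √(2/6) × Γ(3.5)/Γ(3) = 0.959.
- Probability that the SD falls below the true value: P(χ²₆ < 6) = 0.577.
- The variance itself is unbiased at any sample size.

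The plan speaks of a mean standard deviation, which may average two test-versus-control contrasts. Taking 12 degrees of freedom as the most favourable assumption, the two figures are 0.979 and 0.554. In both cases any tendency is slightly downwards, opposite to the plan's claim.

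**How imprecise is 16.1?** The 95% interval is 16.1 × √(df/χ²), with χ² at its 97.5% and 2.5% points.

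- 6 df: 16.1 × √(6/14.449) = 10.4 to 16.1 × √(6/1.237) = 35.5. Power at 20 runs from 98% down to 22%.
- 12 df: 16.1 × √(12/23.337) = 11.5 to 16.1 × √(12/4.404) = 26.6. Power at 20 runs from 96% down to 36%.

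**Sensitivity to the planned analysis.** Section 7.3 says: "If the normality assumption holds, a Linear Mixed Model will be used". The model is not specified. Assume participant, period and lens effects with a residual pooled over three lenses, so df = 2n - 4, and the same SD for every pairwise difference. Power is then 77.1% at 20 (36 df), 79.2% at 21, 81.1% at 22 and 82.9% at 23. Twenty remains below 80%.

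**The other primary endpoint.** Daily wearing time, with SD 0.8 hours, has more than 99.9% power at 20 whether the margin is 1.0 or 2.0 hours. The shortfall concerns visual satisfaction only.

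**The case against.** The strongest reply is that 20 is a floor and not the expected size. Up to 30 may be enrolled, and the plan nowhere says recruitment stops at 20 completers. Reaching 23 from 30 allows 7 losses (7/30 = 23%) over three wear periods of about 10 days. This stands as a limit on the size of the problem. It does not remove it, because the Synopsis requires only 20 and no dropout rate is given from which to expect more.

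A second reply is that the calculation itself is right and that a lower floor was a judgement stated openly beside it. That is fair: the 23 is correct, and the fault lies in the inference from it and in the missing power figure.

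Third, the SD is so uncertain that three participants matter little. On the 6-df interval, power runs from 22% to 98% at 20 and from 25% to 99% at 23. This also stands, and it means that raising the minimum to 23 would not cure the imprecision. But imprecision is no argument for a smaller sample.

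Fourth, the sponsor may know something about the previous study that makes 16.1 too high, and some sections listed in the contents, including 5.2 (Number of Participants), are not in the text available for this review. The sentence in section 7.2, however, argues from the small number alone, and that argument fails under normality.

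**Conclusion.** The concern holds. The required number does not deliver the only power the plan quotes for overall visual satisfaction: 75.0% at 20 against 81.2% at 23, a loss of about 6 percentage points, or 5 below the nominal 80%. Put as risk, each comparison of identical lenses fails to show non-inferiority 25% of the time at the minimum, against the 20% implied by the stated power.

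These figures assume a true SD of 16.1, a true difference of zero and the plan's t-test. Under the assumed mixed model the power at 20 is 77.1%. All are per comparison; the chance of success with both test lenses is lower, and the plan states no joint rule. The statement about over-estimated variability is wrong as a property of small normal samples.

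The margin, decision rule and type I error are sound on this point. It should be corrected, but it does not threaten the validity of a positive finding.

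**What to change.** In section 7.2, remove the claim that seven participants probably overstate the variability and the inference drawn from it. Replace it with wording such as: *The SD of 16.1 comes from seven participants and is imprecise. At this SD, 23 per-protocol participants give 80% power; the minimum of 20 gives about 75%. Up to 30 will be enrolled.*

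Alternatively, set the minimum to the plan's own 23 in both section 7.2 and the Synopsis.

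The first option changes wording only; its cost is that a lower power is stated openly. The second may need up to three more completers, within the existing limits of 40 screened and 30 enrolled. Neither changes the margins or the analysis.
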